### **5.13.2. Adverse Events**

Adverse events are recorded in the eCRFs. Each AE will be coded to system organ class (SOC) and preferred term (PT) using the Medical Dictionary for Regulatory Activities (MedDRA) version that is current at the time of database lock. Severity of AEs is recorded as mild, moderate, or severe.

A TEAE is defined as an event that either first occurred or worsened in severity after the first dose of study treatment and on or prior to the last visit date during the analysis period. The analysis period is defined as the treatment period plus 30 days off-drug follow-up time, except for deaths and malignancies for which the analysis period includes the treatment period and off-drug follow-up time.

Adverse events are classified based upon the MedDRA PT. The MedDRA Lowest Level Term (LLT) will be used in defining which events are treatment-emergent. The maximum severity for each LLT during the baseline period up to first dose of the study medication will be used as baseline. If an event with missing severity is preexisting during the baseline period, and persists during the treatment period, then the baseline severity will be considered mild for determining TEAE (that is, the event is treatment-emergent if the severity is coded moderate or severe postbaseline and not treatment-emergent if the severity is coded mild postbaseline). If an event occurring postbaseline has a missing severity rating, then the event is considered treatment-emergent. The day and time for events where onset is on the day of the first dose of study treatment will both be used to distinguish between pretreatment and posttreatment in order to derive treatment-emergence. Should there be insufficient data for AE start date to make this comparison (for example, the AE start year is the same as the treatment start year, but the AE start month and day are missing), the AE will be considered treatment-emergent.

In an overview table, the number and percentage of subjects who experienced a TEAE or serious adverse event (SAE), died due to an AE, or discontinued from study due to an AE will be summarized by treatment.

The frequency and percentages of patients with TEAEs will be summarized by treatment using MedDRA PT nested within SOC. Events will be ordered by decreasing frequency within SOC. A common TEAEs (at least reported by 5% of patients) summary will also be provided. As an additional table or figure, the percentages of patients with TEAEs will be summarized by treatment using MedDRA PT (without regard to SOC). Events will be ordered by decreasing frequency within PT. The frequency and percentages of patients with TEAEs by maximum severity will also be summarized by treatment using MedDRA PT nested within SOC.

Fisher's exact test will be performed to compare percentages for each LY3375880 dose group and Placebo at both the SOC and PT levels.

Listings will be presented for all AEs, all SAEs, all AEs leading to death, all AEs leading to study drug temporary interruption, and all AEs leading to discontinuation from the study.

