Although the immune-mediated findings in the animal studies are generally not considered predictive for humans and there have been no apparent clinical effects attributable to immunogenicity in Study FCAA, subjects in Study FCAB will continue to be closely monitored for safety events, including allergic/hypersensitivity reactions, injection site reactions, or other events plausibly related to drug immunogenicity. Ongoing monitoring of safety data (including AEs, SAEs, and selected laboratory measurements) will continue throughout the study using blinded data. Interim safety analyses will be conducted to review unblinded safety data if deemed appropriate based on the ongoing blinded monitoring; the unblinded analyses will be conducted and reviewed by an internal assessment committee composed of personnel who do not have direct site contact or data entry/validation responsibilities.

More information about the known and expected benefits, risks, SAEs, and reasonably anticipated AEs of LY3375880 will be found in the Investigator's Brochure (IB).

4. Objectives and Endpoints

Table FCAB.2 shows the objectives and endpoints of the study.

Table FCAB.2. Objectives and Endpoints

Objectives	Endpoints
Primary 
 To compare the efficacy of LY3375880 to placebo as measured by IGA at Week 16 in the treatment of subjects with moderate-to-severe AD. 	
 Proportion of subjects achieving IGA of 0 or 1 with a ≥ 2-point improvement at Week 16.
Secondary 
 To compare the efficacy of LY3375880 to placebo as measured by improvement in signs and symptoms at Week 16 and 52 in the treatment of subjects with moderate-to-severe AD. To characterize the PK of LY3375880 in subjects with moderate-to-severe AD 	
 Proportion of subjects achieving at Week 16 
 EASI-50 EASI-75 EASI-90 SCORAD-75 SCORAD-90 IGA of 0 Mean change from baseline to Week 16 in 
 EASI SCORAD Proportion of subjects achieving IGA of 0 or 1 at Week 52 Serum PK Data

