5.5. Justification for Dose

The LY3375880 dose range of 50 mg to 600 mg SC is based on clinical safety data from the Phase 1 Study FCAA, pharmacokinetic/pharmacodynamic (PK/PD) modeling, and nonclinical toxicology data.

In the Phase 1 study FCAA, single and multiple doses of up to 700 mg IV of LY3375880 were tested in healthy subjects. As of the cutoff date of 06 September 2018, all cohorts have completed dosing. There have been no dose-limiting AEs identified and dose escalation to the highest possible dose of 700 mg IV in both the single ascending and multiple ascending dose portions was achieved. No deaths, SAEs, or discontinuations due to AEs were reported. Overall, the frequency of treatment-emergent AEs was 8/20 (40%) for subjects dosed with placebo and 11/58 (19%) for subjects dosed with LY3375880. There were no dose-related changes in AE frequency across single doses of 3 to 700 mg LY3375880 or multiple doses of 150 to 700 mg LY3375880. To date, the most commonly reported AEs in LY3375880 treated subjects have been upper respiratory tract infection reported by 3 (5.2%) subjects who received LY3375880 and 0 subjects who received placebo, headache reported by 2 (3.4%) subjects who received LY3375880 and 1 (5.0%) subject who received placebo, and skin abrasion reported by 2 (3.4%) subjects who received LY3375880 and 1 (5%) subject who received placebo. The majority of the AEs have been mild and no severe AEs have been reported. There were no clinically significant changes in clinical safety laboratory results in subjects administered LY3375880.

The available PK and target engagement data from the first 6 cohorts of the SAD portion of FCAA (3mg to 400 mg SC and 100 mg IV) as well as data from the first cohort of the multiple ascending dose (150 mg SC) were used to develop a PK/PD model. The model described the time course of the relationship of serum concentrations of LY3375880 and inhibition of IL-33. Based on simulations conducted with this model, doses between 50 mg and 600 mg administered once monthly are expected to cover a minimal-maximal effect range, assuming that maximum inhibition of IL-33 throughout the dosing interval would be required for efficacy.

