9.9. Medical Resource Utilization and Health Economics

Health Economics and Medical Resource Utilization parameters will not be evaluated in this study.

10. Statistical Considerations

Approximately 200 subjects will be randomized at a 1:1:1:1 ratio in the blinded induction dosing period to LY3375880 50 mg, 150 mg, 600 mg, and placebo (50 subjects per dosing regimen).

Assuming 36% and 8% of subjects achieve an IGA score of 0 or 1 (clear or almost clear skin) and ≥ 2 -point improvement from baseline at Week 16 for LY3375880 and placebo, respectively, pairwise comparisons to placebo have at least 90% power using a 2-sided Fisher's exact test at the 0.05 significance level, with no adjustment for multiple comparisons.

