## 5. A Priori Statistical Methods

### 5.1. Determination of Sample Size

Study I9N-MC-FCAB(b) will aim to enroll approximately 200 patients  $\geq 18$  years of age. Assuming 36% and 8% of subjects achieve an IGA score of 0 or 1 (clear or almost clear skin) and  $\geq 2$ -point improvement from baseline at Week 16 for LY3375880 and placebo, respectively, pairwise comparisons to placebo have at least 90% power using a 2-sided Fisher's exact test at the 0.05 significance level, with no adjustment for multiple comparisons.

Sample size and power estimates were obtained from R version 3.4.3.

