### 5.2. General Considerations

This plan describes *a priori* statistical analyses for efficacy, health outcomes, and safety that will be performed.

Statistical analysis of this study will be the responsibility of Eli Lilly and Company (Lilly). The statistical analyses will be performed using SAS® Version 9.4 or higher.

Not all displays described in this SAP will necessarily be included in the clinical study report (CSR). Not all displays will necessarily be created as a “static” display. Some may be incorporated into interactive display tools instead of or in addition to a static display. Any display described in this SAP and not included in the CSR would be available upon request.

For continuous measures, summary statistics will include sample size, mean, standard deviation (SD), minimum, median, and maximum. The 1st quartile and 3rd quartile may also be presented. The minimum and maximum will be reported to the same number of decimal places as the raw data recorded in the database. The mean, 1st quartile, median, 3rd quartile, and SD will generally be reported to 1 more decimal place than the raw data recorded in the database. In general, the maximum number of decimal places reported shall be 4 for any summary statistic. For categorical measures, summary statistics will include the sample size, frequency count, and percentage. Percentages will be presented to 1 decimal place unless otherwise stated.

Percentages will not be presented for zero counts. Incidence rates and 95% confidence interval (CI) will be displayed for select safety endpoints.

Statistical tests of treatment effects and CIs will be performed at a 2-sided significance level of 0.05, unless otherwise stated.

All p-values will be rounded up to 3 decimal places. For example, any p-value strictly greater than 0.049 and less than or equal to 0.05 will be displayed as 0.050. This guarantees that on any printed statistical output, the unrounded p-value will always be less than or equal to the displayed p-value. A displayed p-value of 0.001 will always be understood to mean  $\leq 0.001$ . Likewise, any p-value displayed as 1.000 will be understood to mean  $> 0.999$  and  $\leq 1$ .

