Fisher's exact test will be used for the adverse events (AEs), discontinuation, and other categorical safety data for between-treatment group comparisons. Continuous vital signs, body weight, and other continuous safety variables, including laboratory variables will be analyzed by an ANCOVA with treatment group and baseline value in the model. The significance of within-treatment group changes from baseline will be evaluated by testing whether or not the treatment group LSM changes from baseline are different from zero; the standard error for the LSM change will also be displayed. Differences in LSM will be displayed, with the p-value associated with the LSM comparison to placebo and a 95% CI on the LSM difference also provided. In addition to the LSMs for each group, the within-group p-value for the change from baseline will be displayed. Treatment-emergent high/low for categorical laboratory safety analyses will also be produced.

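### The adverse event tables test each LY3375880 dose against placebo but plan no combined LY3375880 column or test for the Induction Period, so an effect shared by all doses is shown less clearly and less precisely than the data allow

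*SAP*

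**What the plan says.** SAP 5.13.2 (Adverse Events) states that Fisher's "exact test will be performed to compare percentages for each LY3375880 dose group and Placebo at both the SOC and PT levels". SAP 5.13.2.2 repeats the sentence for adverse events that led to permanent discontinuation of treatment.

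Elsewhere the wording is less specific. SAP 5.2.3 assigns Fisher's test to adverse events, "discontinuation, and other categorical safety data for between-treatment group comparisons". The laboratory shift tables in SAP 5.13.3 compare treatments without saying which pairs. SAP 5.13.2.1 (serious adverse events) gives a summary with no test, and SAP 5.13.6.4 (hypersensitivity) gives a listing. Neither document defines a combined LY3375880 group for a test or a summary column.

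On size, Protocol Section 10 says "Approximately 200 subjects will be randomized at a 1:1:1:1 ratio in the blinded induction dosing period", with "50 subjects per dosing regimen". On level, SAP 5.2 says "Statistical tests of treatment effects and CIs will be performed at a 2-sided significance level of 0.05", and SAP 5.6 makes no multiplicity adjustment. Under SAP 5.13, safety subjects are grouped by the product randomized at Week 0.

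**The concern.** Protocol 3.3 names allergic or hypersensitivity reactions and injection site reactions, "or other events plausibly related to drug immunogenicity", as what subjects will be watched for. It does not describe these as rising with dose. Protocol 5.5 reports for Phase 1: "There were no dose-related changes in AE frequency across single doses of 3 to 700 mg LY3375880", and its overall Phase 1 comparison is itself pooled: 11/58 on LY3375880 against 8/20 on placebo. If a harm is common to all doses, the direct question is whether LY3375880 as a whole differs from placebo, and the planned adverse event tables have no row or column that answers it.

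At stake is how the safety tables of the first Phase 2 study of this antibody are read. A shared effect may appear as one significant dose among three, which invites dismissal as chance. It may also appear as three similar excesses, none of them significant.

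**Working it through.** **Inputs.** 50 subjects per arm (Protocol Section 10), so 3 × 50 = 150 on LY3375880 if pooled. Two-sided 0.05 (SAP 5.2). Three unadjusted tests per term (SAP 5.13.2, 5.6). The documents give no planning rates for adverse events in this population, so the rates below are assumptions, with the same raised rate in all three dose arms and no dropout.

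**Method.** Exact power = Σx Σy Bin(x; n1, p1) · Bin(y; n2, p0), summed over outcomes with Fisher p ≤ 0.05. For adverse events, only outcomes with the higher proportion on LY3375880 are counted.

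**Check on the plan's own figure.** SAP 5.1: "Assuming 36% and 8% of subjects achieve an IGA score of 0 or 1" on LY3375880 and placebo, with at least 90% power claimed. The same calculation at 50 v 50 (both directions counted) gives 91.4%, so the claim is reproduced.

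**Three tests sharing one placebo arm.** Let q(y) be the chance that one dose arm is significantly above placebo when placebo has y events.
- At least one significant: Σy Bin(y; 50, p0) · [1 − (1 − q(y))³]
- Two or more: Σy Bin(y; 50, p0) · [3q(y)²(1 − q(y)) + q(y)³]
- All three: Σy Bin(y; 50, p0) · q(y)³

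| Placebo v every dose | One test, 50 v 50 | Pooled, 150 v 50 | One ÷ pooled | At least one of three | All three |
|---|---|---|---|---|---|
| 0% v 8% | 21% | 54% | 0.38 | 50% | 1% |
| 2% v 12% | 31% | 62% | 0.50 | 59% | 7% |
| 5% v 20% | 51% | 76% | 0.67 | 78% | 24% |
| 10% v 25% | 41% | 63% | 0.65 | 67% | 16% |
| 40% v 60% | 46% | 67% | 0.69 | 71% | 22% |
| 2% v 20% | 78% | 97% | 0.81 | 96% | 55% |

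**How isolated the flags are.** Two or more doses are significant in 28% of trials at 2% v 12% and in 11% at 0% v 8%. Exactly one dose is therefore significant in 59 − 28 = 31% and 50 − 11 = 39% of trials. That is about half (31/59) and about four-fifths (39/50) of the trials with any flag.

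**Consistent signal, no flag.** Against 0/50 on placebo:
- 5/50 on each dose gives p=0.056 three times; pooled, 15/150 gives p=0.025.
- 4/50 on each dose gives p=0.117 three times; pooled, 12/150 gives p=0.040.
- The smallest significant count is 6/50 for one dose and 12/150 pooled.

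**Precision.** With a common rate, the ratio of standard errors is √[(1/150 + 1/50) ÷ (1/50 + 1/50)] = √(0.0267/0.04) = 0.82, so the pooled difference has a standard error about 18% smaller. With no event seen, the one-sided 95% upper limit is 1 − 0.05^(1/50) = 5.8% for one dose and 1 − 0.05^(1/150) = 2.0% pooled.

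**Dilution.** If only 600 mg carries the effect (20% there, 2% in the other three arms), the 600 mg test has 78% power and the pooled test 23%.

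**The case against.** The strongest reply is that the power of a single test is the wrong yardstick. The plan runs three tests, and the chance that at least one is significant is 0 to 4 percentage points below the pooled power for uncommon events and slightly above it for commoner ones. This stands. A reader might infer from the single-test column that the plan has about half the power the data could give; it does not support that. Even for one test, half applies only to uncommon events with modest increases. For commoner events or large effects one test has about 60% to 80% of the pooled power.

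The scope is also limited. Testing each dose is explicit only for treatment-emergent events and discontinuations, so it would be wrong to say that all safety tests are per-dose.

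The premise of no dose relation is weak as well. It rests on 58 healthy volunteers and on the protocol's silence about dose ordering, whereas Protocol 5.4 uses a broad dose range to characterise benefit and risk. Per-dose tests fit that aim, and the dilution figure shows why they must stay.

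Finally, the named risks have other safeguards: extra case report form questions, listings of hypersensitivity events, and possible unblinded committee review. Counts appear by treatment, so a reader can add the columns. That last point holds for counts, but it leaves any pooled comparison to be made after the data are seen.

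**Conclusion.** The point holds as a gap in presentation and precision, not as an error in the planned tests or a large loss of detection. No combined LY3375880 comparison is planned. For an uncommon event raised equally at all doses, the planned tables will often show one isolated significant dose, and sometimes none while the pooled comparison is significant. The shared effect is also estimated with a larger standard error than necessary: the pooled one is about 18% smaller.

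This rests on 50 subjects per arm, the assumed event rates, and an equal effect across doses. The documents neither establish nor exclude an equal effect, so they do not support making the pooled test the main safety analysis. The zero-event limits illustrate precision; the SAP plans no such limit, so they do not show that any planned statement is wrong.

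**What to change.** For the Induction Period only:

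- SAP 5.13.2 and 5.13.2.2, and the categorical shift tables in 5.13.3: add an 'All LY3375880' column (the three randomized doses combined) and a Fisher test of that column against placebo.
- SAP 5.13.2.1: add the column alone, since no test is planned there.
- Keep every per-dose column and test, and state that the pooled test supplements them.

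The limit to induction is needed because from the Week 16 visit placebo subjects can move to LY3375880 and LY3375880 responders can be re-randomized to placebo. Grouping by Week 0 assignment then no longer separates exposed from unexposed subjects.

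The cost is one extra column and, where a test is added, one more unadjusted p-value per row. With no true difference, the pooled Fisher test rejects in 3.1% of trials at a 5% event rate and 4.4% at a 40% rate. The downside is dilution of an effect confined to 600 mg, which the retained per-dose tests cover. The change should be written in before unblinding.

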#### **5.13.2.1. Serious Adverse Event Analyses**

The number and percentage of patients who experienced an SAE (including the SAEs that led to death) during the study drug period will be summarized by treatment using MedDRA PT nested within SOC. Events will be ordered by decreasing frequency within SOC.

#### **5.13.2.2. Other Significant Adverse Events**

The number and percentage of patients who permanently discontinued from study treatment due to an AE (including AEs that led to death) during the study drug period will be summarized by treatment using MedDRA PT nested within SOC. Events will be ordered by decreasing frequency within SOC.

Fisher's exact test will be performed to compare percentages for each LY3375880 dose group and Placebo at both the SOC and PT levels.

### **5.13.3. Clinical Laboratory Evaluation**

Laboratory analyses will include planned analytes only. Planned analytes are those specified in the protocol. Summaries will be provided in both Système International (SI) and United States (US) conventional (CN) units (when different). Limits from the performing lab will be used to define low and high. Analyses of laboratory values will be produced using the measurements collected at scheduled time points. All unscheduled assessments will appear only in data listings.

- **Box plots for observed values:** Values at each visit (starting at randomization) will be displayed in box plots for patients who have both a baseline and a result for the specified visit. Unplanned measurements will be excluded. Original-scale data will be used for the display. These box plots will be used to evaluate trends over time and to assess a potential impact of outliers on central tendency summaries. The box plot will be a

notched box for each treatment with outliers displayed, individual measurements outside of reference limits will also be displayed using distinct symbols overlaying the box plot, and descriptive summary statistics will be included in a table below the box plot.

- **Box plots for change values:** Change from baseline to each visit will be displayed in box plots for patients who have both a baseline and a result for the specified visit. Change from baseline to last observation will also be summarized and analyzed for patients who have both baseline and at least 1 postbaseline result. Baseline will be the last non-missing observation in the baseline period. The last non-missing observation in the Dosing Period will be used as the last observation. Unplanned measurements will be excluded. The box plot will be a notched box for each treatment with outliers displayed, change from baseline to last observation will be summarized within the box plot of changes (rightmost column), and descriptive summary statistics will be included in a table below the box plot, along with a p-value using the ANCOVA model containing terms for treatment and the continuous covariate of baseline measurement. Type III sums of squares will be used. The significance of within-treatment group changes from baseline will be evaluated by testing whether the treatment group LSMean changes from baseline are different from zero using a t-statistic. In addition to the LSMeans and tests, the SD, minimum, Q1, median, Q3, and maximum will be displayed.
- **Outlier/shift displays focusing on low values (where low values are of interest):** A scatterplot, a shift table, and a shift to low table will be created for both the Induction and Maintenance Period. Unplanned measurements will be included. The scatterplot will plot the baseline value versus the minimum value during the study period. Lines indicating the reference limits will be included. In cases where limits vary across demographic characteristics, lines indicating the most common limit will be displayed. The shift table will include the number and percentage of patients within each baseline category (low, normal, high, or missing) versus each postbaseline category (minimum value is low, normal, high, or missing) by treatment. Patients in the safety population will be included in the shift table. The shift from normal/high to low table will include the number and percentage of patients by treatment whose baseline result is normal or high and whose minimum treatment result is low. Patients whose baseline result is normal or high and have at least 1 post-baseline result during the study period are included. The Fisher's exact test will be used to compare percentages of patients who shift from normal/high to low between treatments.
- **Outlier/shift displays focusing on high values (where high values are of interest):** The same approach described for low values will be used, except maximum values will replace minimum values.

Alanine aminotransferase (ALT), aspartate aminotransferase (AST), and total bilirubin will not be included in this analysis as different ranges will be used as described in Section 5.13.5.

